9.1. Secondary Efficacy Endpoints

Objective Response Rate (ORR): Patient listings of tumor response outcomes (CR, PR, non-CR/non-progressive disease, stable disease, progressive disease, unevaluable, or not assessed) at study visits, as well as best overall response per RECIST v1.1, will be presented by treatment regimen dose group and overall for the ITT population. By-group summary tables will include distribution of response outcomes, best overall response derived over all visits, and point estimates with Clopper-Pearson² 95% CIs for ORR, defined as the proportion of patients with an objective tumor response (either PR or CR) in patients with measurable disease, including best radiographic response for soft tissue.

For supportive purposes, best overall response and point estimates with Clopper-Pearson 95% CIs for ORR will also be summarized using confirmed response.

PSA Levels: PSA levels recorded at each visit will be listed. Proportions of patients in the Safety population who experience a 50% or greater reduction in PSA levels at any visit since baseline will be reported with Clopper-Pearson 95% CIs by treatment group and overall. Mean reduction levels will be characterized via summary statistics. Median time from date of first dose of exicorilant to PSA progression (first occurrence of 50% or greater increase in PSA levels), along with 95% CIs will be estimated via Kaplan-Meier method, and also plotted graphically by treatment group. Patients who are alive and progression-free will be censored at the date of their-last PSA evaluation.

In dose escalation and expansion phases separately, best PSA response will be illustrated graphically via waterfall plots. For each patient, the maximum percent change in PSA levels since baseline will be depicted on the response axis, with vertical bars below the baseline representing decline in the blood-based marker.

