Symptomatic Skeletal Event (SSE): SSE is defined as symptomatic fracture, radiation or surgery to bone, or spinal cord compression. SSEs include only symptomatic events of clear clinical significance. Kaplan-Meier estimates of median time from date of first dose of exicorilant to the first occurrence of SSE and associated 95% CIs, will be computed by treatment regimen dose group and overall for the Safety population. Patients who are event-free will be censored at the date of their end of study/treatment + 30 days visit. Kaplan-Meier graph of the probability of the event will also be constructed by treatment group.

Radiographic progression-free survival (rPFS): For the Response-Evaluable population, rPFS will be determined from the first dose of study treatment (exicorilant and/or enzalutamide) to the date when the first site of disease is found to progress on CT, MRI, or radionucleotide bone scan per PCWG3, or death, whichever occurs first. Progression will be assessed by the Investigator using RECIST v1.1.

$$\text{rPFS (months)} = (\text{earliest date of progression, death, or censoring} - \text{date of first study treatment} + 1) / 30.4375$$

Patients who do not experience disease progression or death (due to any cause) will be right-censored at the time of the last tumor assessment date. Censoring date will be based on the date patient was last known to be alive and progression-free (i.e., last assessment date) or data analysis cutoff date, whichever occurs first. Censoring rules are summarized in [Table 3](#) below.

Table 3: Censoring Rules for the Primary Analysis of PFS

Censoring Categories	Date of Censoring
Patients who did not have baseline or postbaseline tumor assessments and did not die on or before the data cutoff date	Date of first study treatment

Patients who did not have disease progression as determined by the Investigator and did not die on or before the data cutoff date	Date of the last adequate tumor assessment on or before the data cutoff date
Patients who did not have disease progression as determined by the Investigator on or before initiation of subsequent anticancer therapy for prostate cancer and did not die on or before the data cutoff date	Date of the last adequate tumor assessment on or before initiation of subsequent anticancer therapy and on or before the data cutoff date

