Patients who had 2 or more consecutive missed scheduled tumor assessments immediately prior to disease progression	Date of the last adequate tumor assessment without evidence of disease progression before the 2 missed tumor assessments and on or before the data cutoff date
Patients who did not have disease progression as determined by the Investigator and died more than 119 days from most recent tumor assessment.	Date of the last adequate tumor assessment on or before the data cutoff date

Note: If a patient meets the criteria for more than 1 censoring rule, PFS will be censored at the earliest censoring date.

Kaplan-Meier curves will be plotted by treatment regimen dose groups, and the estimate of median rPFS time (months) with 95% CI will be ascertained. For each cohort, progression-free rate at 4, 6, and 12 months will also be summarized.

Duration of response (DOR): Duration of response will be defined for patients in the Response-Evaluable population as the time from the first occurrence of a documented objective tumor response of CR or PR to the time of radiographic progression (per Investigator using RECIST v1.1) or death from any cause on study, whichever occurs first. Patients who have not experienced disease progression or death will be censored at the time of the last tumor assessment date. Date of censoring will be determined according to same rules as described for rPFS endpoint.

$$\text{DOR (months)} = (\text{earliest date of progression, death, or censoring} - \text{date of first documented objective response} + 1) / 30.4375$$

Kaplan-Meier graph will be plotted by treatment group and estimates of median duration with 95% CIs will be obtained for each dose cohort and overall. Patients who do not achieve a tumor response of CR or PR, will be excluded from this analysis.

Clinical progression: For the Response-Evaluable population, clinical disease progression, defined as time from first dose of study treatment (exicorilant and/or enzalutamide) to date of treatment discontinuation due to disease progression, will be estimated via the Kaplan-Meier

method. Patients who are alive and progression-free will be censored at their end of study visit. Median time to progression and associated 95% CIs will be summarized, overall and by treatment group. Kaplan-Meier graph of the probability of the event will also be plotted by treatment group.

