Bone disease progression: For the Response-Evaluable population, bone disease progression, defined as time from first dose of study treatment (exicorilant and/or enzalutamide) to first confirmed appearance of at least 2 new bone metastatic lesions, will be estimated via the Kaplan-Meier method. Cases of equivocal progression will be confirmed by a repeat scan 8 weeks later. Patients who are alive and progression-free will be censored at their end of study visit. Median time to progression and associated 95% CIs will be summarized, overall and by treatment group. Kaplan-Meier graph of the probability of the event will also be plotted by treatment group.

Overall survival (OS): Overall survival will be calculated as the time from the first dose of study treatment (exicorilant and/or enzalutamide) to the date of death from any cause. Deaths that occur on or before the data cutoff date will be considered an event. If a patient has not died before the analysis cutoff date, OS will be censored at the date of last contact on or before the data cutoff date. The last contact date will be derived as follows:

Source Data Conditions	Source Data Conditions
Date of randomization	No condition
Last contact date/last date patient known to be alive from Long-Term Follow-Up eCRF	Use if patient status is reported to be alive Do not use if patient status is reported unknown
End of study	Not lost to follow up
Start/end dates of postbaseline antineoplastic therapy	Nonmissing medication/procedure term
Start/end dates from drug administration record	Nonmissing dose. Doses of 0 are allowed.
End of treatment date from the End of Treatment eCRF	No condition
Investigator overall tumor response assessment date	Evaluation is marked as done.
Laboratory/PK collection dates	Sample collection marked as done.
Vital signs date	At least 1 nonmissing parameter value
ECOG performance status date	Nonmissing ECOG performance status
Start/end dates of adverse events	Nonmissing verbatim term
Physical examination	Evaluation is marked as done.
ECG	Evaluation is marked as done.

The OS in months is defined as follows:

$$\text{OS (months)} = (\text{earliest date of death or censoring} - \text{date of first study treatment} + 1) / 30.4375$$

Median, 25th and 75th percentiles of OS, in months, with 95% CIs will be summarized and plotted graphically by treatment arm and overall using the Kaplan-Meier method.

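### SSE is plotted as a Kaplan-Meier event probability with deaths implicitly censored, which overstates it; PSA, clinical and bone progression give no rule for deaths

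*SAP*

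**What the plan says.** All four endpoints are in SAP 9.1, Secondary Efficacy Endpoints.

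- **SSE.** "SSE is defined as symptomatic fracture, radiation or surgery to bone, or spinal cord compression"; death is not a component. The censoring rule is "Patients who are event-free will be censored at the date of their end of study/treatment + 30 days visit". A median with 95% CI is planned, and "Kaplan-Meier graph of the probability of the event will also be constructed by treatment group".
- **PSA progression.** Median time "will be estimated via Kaplan-Meier method, and also plotted graphically by treatment group". The censoring rule is "Patients who are alive and progression-free will be censored at the date of their-last PSA evaluation".
- **Clinical progression.** Time from first dose "to date of treatment discontinuation due to disease progression, will be estimated via the Kaplan-Meier" method. The censoring rule is "Patients who are alive and progression-free will be censored at their end of study visit", and "Kaplan-Meier graph of the probability of the event will also be plotted by treatment group".
- **Bone disease progression.** The event is the first confirmed appearance of two or more new bone lesions. The censoring and graph sentences are the same as for clinical progression.

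The same section does assign deaths for rPFS, duration of response and overall survival, where death is an event. SAP Table 3 even has a rule for deaths long after the last scan. SAP 3.2 makes the proportion of patients free of PSA, bone and clinical progression at 4, 6 and 12 months part of a secondary objective. Neither document plans a competing-risk or cumulative-incidence method.

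**The concern.** A patient who dies without an SSE can no longer have one. If he is censored, Kaplan-Meier treats him as still able to have the event later, at the same rate as the survivors. One minus Kaplan-Meier then describes a setting without death, and it exceeds the proportion of patients who actually have an SSE. The SAP nevertheless labels the SSE curve as the probability of the event.

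The other three endpoints have a different defect. Their censoring sentence applies only to patients who are alive without progression, and their event definitions do not include death. A patient who dies first therefore has neither an event nor a censoring date. The rPFS paragraph also refers to patients being alive and free of progression, and there death is an event. Two programmers could handle deaths differently and both cite the SAP. The proportions at 4, 6 and 12 months would then depend on an unwritten choice.

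**Working it through.** **Inputs.** The documents give no rates, sample size or power for these endpoints, so there is no planned figure to reproduce. The following are assumptions for illustration: constant, independent monthly hazards *l* (event) and *m* (death without the event), each equal to −ln(1 − 12-month risk)/12; a 12-month event risk of 30%; 12-month death risks of 10% to 40%; deaths followed. The n of 20 is the approximate size of one expansion cohort (SAP 5).

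**Formulas at time T.**

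- 1 − KM, deaths censored: 1 − exp(−*l*T)
- Cumulative incidence: *l*/(*l*+*m*) × [1 − exp(−(*l*+*m*)T)]
- Composite, death counted as an event: 1 − exp(−(*l*+*m*)T)
- Greenwood SE of KM, deaths as censoring: exp(−*l*T) × √{ *l*/(*l*+*m*) × [exp((*l*+*m*)T) − 1]/n }

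**SSE, worked case with both risks 30%.** Here *l* = *m*, so *l*/(*l*+*m*) = 0.5. At 12 months exp(−*l*T) = 0.70 and exp(−(*l*+*m*)T) = 0.70 × 0.70 = 0.49.

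- 1 − KM = 30.0%.
- Cumulative incidence = 0.5 × (1 − 0.49) = 25.5%, a gap of 4.5 points.
- SE = 0.70 × √[0.5 × (1/0.49 − 1)/20] = 0.113, so the gap is 4.5/11.3 = 0.40 SE.

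The same formulas over the range of death risks, with the event risk held at 30%:

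| 12-month death risk | 1 − KM, 12 mo | Cumulative incidence, 12 mo | Gap (points) | Gap/SE, n = 20 | 24 mo: 1 − KM vs cumulative incidence |
|---|---|---|---|---|---|
| 10% | 30.0% | 28.6% | 1.4 | 0.14 | 51.0% vs 46.6% |
| 20% | 30.0% | 27.1% | 2.9 | 0.27 | 51.0% vs 42.2% |
| 30% | 30.0% | 25.5% | 4.5 | 0.40 | 51.0% vs 38.0% |
| 40% | 30.0% | 23.8% | 6.2 | 0.52 | 51.0% vs 33.9% |

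The gap is small early. With both risks at 30% it is 11.2% vs 10.6% at 4 months and 16.3% vs 15.0% at 6 months. It grows with follow-up: at 24 months it is 0.94 SE with both risks at 30%, and about 1.1 SE with a 40% death risk.

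The planned median is also affected. With a 40% death risk the Kaplan-Meier median is ln 2/*l*, just under 24 months, although only *l*/(*l*+*m*) = 41% of patients would ever have the event.

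**PSA, clinical and bone progression.** Take a 30% event risk and a 20% death risk at 12 months. The same patients give:

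- 30.0% if deaths are censored at death;
- 27.1% if the dead stay in the risk set to the administrative end of follow-up, which equals the cumulative incidence;
- 1 − 0.70 × 0.80 = 44.0% if death counts as an event.

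A simulation of 400,000 patients agrees with all three. The SAP does not choose among them.

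**The case against.** The strongest reply has five parts.

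1. **The SAP does not say that SSE deaths are censored.** True; it is an inference. But the rule covers every event-free patient without exception and death is not in the definition, so it is the natural reading. A patient who dies before the named visit also has no such date.
2. **A reader might infer that all four event probabilities are overstated.** The documents do not support that. For PSA, clinical and bone progression no rule is given. Counting death as an event would give a valid composite, and keeping the dead at risk would give no overstatement. The probability-of-the-event label is also not used for PSA progression. For these three the defect is a missing rule.
3. **The size rests on assumed rates.** This stands. The 24-month figures also lie beyond the 4, 6 and 12 months named in SAP 3.2, and that list does not extend to SSE. Nor should a composite be set against a cumulative incidence as if the difference were an error (58% against 24% at 12 months with 30% and 40% risks): they are different quantities.
4. **The calculation assumes deaths are followed.** If SSE follow-up stops at the visit 30 days after treatment, later deaths and later SSEs both drop out. This stands, and it is why the censoring date must be settled together with the handling of death. For clinical progression, stopping treatment for another reason also prevents the event, and the same edit could address that.
5. **Kaplan-Meier is the prespecified descriptive method.** With deaths censored it is interpretable if labelled event-specific. That is a reason to keep it as a supplement, not to call it the probability of the event.

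**Conclusion.** The concern holds in two distinct parts. For SSE, the rule followed as written yields a curve that overstates the probability of an SSE whenever deaths occur first within follow-up. On the assumed risks the excess is about 1 to 6 points at 12 months, below one standard error at n = 20, and larger later. For PSA, clinical and bone progression, deaths without the event are unassigned. The direction of error is undetermined, and the results behind a stated secondary objective cannot be programmed in a unique way.

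The direction for SSE needs only that deaths are censored and the curve is read as labelled. The size depends on the assumed constant, independent hazards and cannot be derived from the documents. These are descriptive secondary endpoints: dose decisions rest mainly on DLTs, tolerability, PK and PD, and the expansion criteria use PSA response, so no test, sample size or dose decision is affected.

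**What to change.** In SAP 9.1, before unblinding:

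- **SSE:** treat death without an SSE as a competing event and report Aalen-Johansen cumulative incidence with 95% CI, by group and overall.
- **PSA, bone and clinical progression:** apply the same method, so that every death has a status and a date, with estimates at 4, 6 and 12 months. State whether a patient who died without the event counts as progression-free at those times.
- **Kaplan-Meier:** keep it as a supplement labelled event-specific, with deaths censored at the date of death.
- **SSE censoring date:** the visit named in the rule can be read as end of study or as 30 days after end of treatment, while Protocol 7.5 continues SSE follow-up after treatment. Reconcile the two so that deaths and SSEs are counted over the same follow-up.

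The cost is a few sentences, a little more programming with a standard procedure, and slightly different descriptive figures. Death dates are already collected in survival follow-up (Protocol 7.5.2).

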enzalutamide 160 mg QD. Twelve patients have received CORT125281 in combination with enzalutamide, and 2 patients discontinued the study during the enzalutamide lead-in and did not receive CORT125281. In Cohort 1, two patients received CORT125281 180 mg BID with enzalutamide. Both patients experienced dose-limiting toxicities (DLTs), including Grade 3 fatigue (n=1), and the concurrent SAEs of Grade 3 fatigue and Grade 3 musculoskeletal pain (n=1); thus CORT125281 180 mg BID was deemed intolerable. A lower dose (CORT125281 140 mg BID) was evaluated in Cohort 2. In Cohort 2, 1 of 3 patients experienced a DLT (SAE of Grade 3 acute pancreatitis). After the third patient enrolled to Cohort 2, an interim assessment of PK and safety was conducted. Based upon the absence of a clinically significant drug interaction of CORT125281 on enzalutamide exposure, enrollment to the subsequent cohort was initiated to further evaluate the CORT125281 140 mg BID dose level without the enzalutamide lead-in. Seven patients have been enrolled to Cohort 3. One patient was not evaluable for DLTs due to disease progression during Cycle 1. Of the 6 remaining patients, no DLTs were observed and the dose was considered tolerable.

Twelve patients (100%) who have received at least 1 dose of CORT125281 in combination with enzalutamide reported greater than 1 TEAE. Five patients (42%) reported TEAEs of Grade 3 or greater considered related to CORT125281; the most frequent TEAE of Grade 3 or greater was fatigue (n=2; 17%). An alternative schedule (once daily [QD] dosing of CORT125281) is planned to optimize the biologically active dose prior to proceeding to the Phase 2 expansion cohorts.

CORT125281-602

In accordance with the study design, 6 healthy subjects received a single oral dose of [¹⁴C]-CORT125281 360 mg (6 × 60-mg capsules). No TEAEs were reported in this study.

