9.2 Analysis Populations and Subgroups

The following populations will be defined for this study:

- The Safety Population will include all patients who received at least 1 dose of CORT125281. All safety analyses, except evaluation of DLTs, will be based on the Safety Population.
- The DLT-Evaluable Population will include all patients in the Dose-Determination Phase cohorts who receive at least 1 dose of CORT125281 and fulfill at least 1 of the following:
 1. Complete at least the following durations of study treatment:
 - a. Segment 1: 28 days of continuous treatment with CORT125281 + enzalutamide
 - b. Segment 2: 3 cycles (≥ 84 days) of CORT125281 + enzalutamide
 2. Experience a DLT within the DLT-evaluation period (Segment 1: 28-days DLT-evaluation period; Segment 2: 3-cycles (≥ 84 -days) DLT-evaluation period).

Patients who have received $<75\%$ of the study regimen due to reasons other than toxicity or who withdraw from the study prior to completion of the DLT-evaluation period for reasons other than toxicity will be considered non-evaluable for DLTs.

- The Response-Evaluable Population (for ORR) will be the subset of the Safety Population with measurable disease at baseline and at least 1 post-baseline tumor assessment.

- The PK-Evaluable Population will be a subset of the Safety Population and will include all patients receiving active study treatment and having any measurable plasma concentration of study treatment at any time point. Prematurely discontinued patients and patients with missing sample concentrations will be included in the PK analyses provided their PK parameters can be adequately characterized based upon the remaining data.

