6.1. Intent-To-Treat Analysis Population

Intent-to-Treat Population (ITT): All patients who received at least 1 dose of the combination (exicorilant + enzalutamide) study treatment. The ITT Population will be used for efficacy analyses.

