6.2. Safety Analysis Population

Safety Population: All patients who received at least 1 dose of exicorilant. All safety analyses, except evaluation of DLTs, will be based on the Safety Population.

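### OS and time to clinical progression start at the enzalutamide lead-in although entry to analysis requires exicorilant, so Segment 1 lead-in patients carry 28 guaranteed event-free days

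*SAP*

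**What the plan says.** **Time origin (SAP 9.1).**
- OS: "Overall survival will be calculated as the time from the first dose of study treatment (exicorilant and/or enzalutamide".
- Clinical progression: "defined as time from first dose of study treatment (exicorilant and/or enzalutamide) to date of treatment discontinuation due to disease progression".
- Bone progression: "defined as time from first dose of study treatment (exicorilant and/or enzalutamide) to first confirmed appearance" of new bone lesions.
- rPFS: "rPFS will be determined from the first dose of study treatment (exicorilant and/or enzalutamide".

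**Entry to the analysis.**
- ITT (SAP 6.1): "All patients who received at least 1 dose of the combination (exicorilant + enzalutamide) study treatment".
- Safety (SAP 6.2): "All patients who received at least 1 dose of exicorilant".
- SAP 9.1 names the Response-Evaluable set for rPFS, clinical and bone progression. It is defined only in Protocol 9.2, where it "will be the subset of the Safety Population with measurable disease at baseline and at least 1 post-baseline tumor assessment".
- SAP 9 also names ITT for the efficacy objectives. Under either set a patient must have had exicorilant.

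**Lead-in.** Protocol 5.3.1 and 7.2 give Segment 1 patients enzalutamide alone from Day -28, for 28 days. SAP 8.8 records that Cohort 3 had no lead-in. Protocol 1.3.2.1 reports that "2 patients discontinued the study during the enzalutamide lead-in and did not receive CORT125281".

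**Other anchors in the same SAP.** Study day, baseline and the treatment-emergent period (7.2), PSA progression and SSE (9.1) all run from first exicorilant. Section 13 lists the baseline and treatment-emergent changes and says nothing about the four origins above.

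**The concern.** When the clock starts before the condition for entering the analysis is met, the interval between the two is guarantee time (immortal time). Patients who fail in that interval are dropped, and those who pass through it keep the time as event-free follow-up. The error can only flatter the estimates.

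At stake are the median and quartiles of OS, the median time to clinical progression, and the 4-, 6- and 12-month progression-free proportions that SAP 3.2 names among its objectives. Cohorts 2 and 3 received the same doses of both drugs and differ in the lead-in, so their curves would be offset by almost a month. If the two cohorts are shown as one dose group, curves with different origins are mixed. Within one patient, time to PSA progression and time to clinical progression would start 28 days apart.

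**Working it through.** **1. Length of the guaranteed interval.** The plan's own figure is 28 days. Day -28 to Day -1, with no Day 0 (SAP 7.2), is 28 days. With the SAP's conversion, 28 / 30.4375 = 0.92 month.

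**2. Who is affected (Protocol 1.3.2.1; SAP 8.8 for the lead-in).**
- Enrolled in Segment 1: 14. Treated with exicorilant: 2 + 3 + 7 = 12. Lost before exicorilant: 14 - 12 = 2.
- Enrolled with a lead-in: 14 - 7 (Cohort 3) = 7. Of these, 7 - 2 = 5 were treated.
- Affected share of treated Segment 1 patients: 5/12 = 42%. Removed by the entry rule: 2/7 = 29% of lead-in patients.
- For clinical progression 5 is an upper bound, because the Response-Evaluable set also needs measurable disease and the documents do not give that count.

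**3. Could an event in the lead-in be counted?**

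| Endpoint | Event in Days -28 to -1 | Can it enter the analysis? |
|---|---|---|
| OS | Death | No: no exicorilant, so not in ITT |
| Clinical progression | Treatment stopped for progression | No: under Protocol 4.4.1 stopping enzalutamide also ends CORT125281 |
| rPFS | Death | No |
| rPFS, bone progression | Progression on a scan | Only through an unscheduled scan in a patient kept on by agreement |

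On the last row: the first scan is due at 8 weeks with a window of 14 days, so no earlier than day 56 - 14 = 42 from first enzalutamide, after the lead-in has ended. Protocol 6.7 allows scans when clinically indicated, and Protocol 4.4.1 lets a progressing patient remain by agreement. A counted event is therefore very unlikely but not excluded.

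**4. Landmarks.** For lead-in patients the 4-, 6- and 12-month points fall at 4 - 0.92 = 3.08, 6 - 0.92 = 5.08 and 12 - 0.92 = 11.08 months from first exicorilant.

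**5. Illustration.** The documents give no expected medians for these endpoints. Assume exponential times from first exicorilant, S(t) = exp(-t ln2 / m), with the same m in all cohorts. Compare S(4) with S(4 - 0.92), and weight 5/12 and 7/12 for the pooled curve.

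| Assumed median m (months) | Lead-in median as reported | Pooled median | 4-month rate from first exicorilant | 4-month rate as reported, lead-in | 4-month rate, pooled |
|---|---|---|---|---|---|
| 3 | 3.92 | 3.41 | 39.7% | 49.1% | 43.6% |
| 6 | 6.92 | 6.40 | 63.0% | 70.1% | 65.9% |
| 9 | 9.92 | 9.39 | 73.5% | 78.9% | 75.7% |
| 12 | 12.92 | 12.39 | 79.4% | 83.7% | 81.2% |

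Over this range the lead-in 4-month rate is 4.3 to 9.4 points too high and the pooled median about 0.4 month too long.

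**6. Food-effect subcohort.** These patients take exicorilant on Day -7 and first take enzalutamide on Cycle 1 Day 2 (SAP 2.4). They meet the ITT condition 8 days after the OS clock starts: 8 / 30.4375 = 0.26 month. Moving the origin to first exicorilant would leave that gap in OS.

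**The case against.** The strongest case is that the present origin is deliberate and, for the scan-based endpoints, sensible.

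- Protocol 9.5.5 defines rPFS and OS from the first dose of either drug, and SAP 4.2.2 repeats it. This is true, and it means the SAP follows the protocol. It does not remove the problem, because the protocol's own analysis sets also require CORT125281. For clinical progression Protocol 9.5.5 gives no origin, so that choice is the SAP's.
- Segment 1 baseline imaging is taken up to 28 days before first enzalutamide, and later scans are counted from first study treatment. Moving the rPFS origin to Cycle 1 Day 1 could leave baseline imaging 28 + 28 = 56 days before time zero. It would also put the first scheduled scan at 56 - 28 = 28 days in lead-in patients against 56 days in Cohort 3. This stands, although Protocol 6.7 also bases scan timing on Cycle 1 Day 1. It is a good reason not to move rPFS and bone progression outright.
- The Response-Evaluable set requires a post-baseline scan, so it builds in guarantee time whatever the origin. This also stands. The change proposed here removes the lead-in credit and not that requirement.
- The numbers are tiny, the summaries are descriptive, no test between cohorts is planned, and the recommended dose rests on tolerability, PD and PK. All true. With five patients, one patient is 20 percentage points, more than any shift in the illustration. This limits the weight of the point. It does not justify a known one-directional error that wording can remove.

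**Conclusion.** The point holds for OS and time to clinical progression: 28 days (0.92 month) of guaranteed event-free time for each Segment 1 lead-in patient, affecting at most 5 of 12 treated. The estimates for Cohorts 1 and 2 and for pooled Segment 1 are too favourable, and Cohort 2 is offset against Cohort 3. The 28 days and the counts come from the documents. The changes in rates and medians rest on the assumed exponential times.

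A reader might infer more than the documents support:
- That all four endpoints are equally affected. For radiographic and bone progression an event in the lead-in is practically but not strictly impossible, and the origin matches the imaging baseline.
- That the two patients who left during the lead-in had progressed or died. No reason is given.
- That these origins were overlooked when baseline was moved. Following the protocol explains OS and rPFS at least as well.
- That the 28-day credit reaches other parts of the study. Cohort 3, Segment 2, the ARant-Resistant Cohort and the non-food-effect Abi-Resistant patients have no lead-in, and the food-effect gap is 8 days.

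**What to change.** 1. In SAP 9.1 start OS and clinical progression on the date the patient qualifies, defined as the first date on which he has received both drugs on study. That is Cycle 1 Day 1 for Segment 1 lead-in patients and Cycle 1 Day 2 for the food-effect subcohort. Restrict both analyses to patients who have such a date.
2. Change the OS formula in SAP 9.1 and the OS definition in SAP 4.2.2 to match, and list the change in Section 13.
3. For rPFS and bone progression keep the origin tied to the imaging baseline. Add a sensitivity analysis from the qualifying date, or with left truncation at that date (the patient joins the risk set only then). Report the 4-, 6- and 12-month rates for the lead-in cohorts on both origins.

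Cost: SAP wording and one extra set of summaries. OS and clinical-progression times become about 0.9 month shorter for about 5 patients, and OS times 8 days shorter for food-effect patients. The SAP would depart from Protocol 9.5.5 on the OS origin, which is why Section 13 must say so.

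An alternative is to keep the origin and analyse everyone who received any study treatment. That brings back the two patients lost in the lead-in, but they discontinued the study, so their later follow-up may not exist.
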